cCTA: The CT portion of the exam will be obtained first. Intravenous esmolol (500 mcg/kg over 1 min and then 100-250 mcg/kg/min) will be administered before the scan to reach a target heart rate of 65 beats per minute. Blood pressure monitoring will occur at each level to ensure systolic blood pressure stays above 100mmHg. Sublingual nitrate (0.4 mg) will be given immediately before the exam.

Scout imaging and non-contrast AC CT scan will be obtained. Then a noncontrast CT coronary calcium (CAC) examination (EKG-gated, sequential) will be performed. Subsequently, iodinated contrast will be infused (100 mL at 4 mL/sec) intravenously followed by a 50 mL saline bolus at the same injection rate and the cCTA performed.

Stress PET: After a 10 minute delay, to allow the heart rate to return to baseline, regadenoson will be hand injected continuously (prefilled syringe: 0.4 mg / 5 mL) over 10 seconds. After an additional interval of 15-20 seconds, 10-12 mCi N-13 ammonia will be hand injected as a bolus followed by immediate injection of 10 mL saline solution over 30 sec. PET emission scan in list mode will be started scan exactly with or seconds before N-13 ammonia injection.

Rest PET: Approximately 30-40 minutes later, to allow sufficient decay of N-13 ammonia to avoid residual activity in the heart, we will perform the rest imaging. A repeat non-contrast AC CT scan will be obtained and the rest PET N-13 ammonia perfusion imaging will be performed. After intravenous injection of \approx 10-12 mCi of N-13 ammonia, PET acquisition over 10 minutes in list mode will be conducted.

If the subject has previously undergone cCTA imaging within 1 month of the scheduled invasive coronary angiogram, the cCTA component of the above examination (to include the CAC) will not be performed.

VI. Image Analysis:

The cCTA will be reviewed by a cardiac CT radiologist ([name]) using a Vital Images workstation for epicardial coronary artery stenoses $\geq 50\%$ diameter. In these lesions $\geq 50\%$ diameter, CT-FFR will be calculated using a computational flow/AI FFR program (Siemens). CAC score will also be obtained using Vital Images software. Segmental MBF at stress and rest, and MPR will be calculated using QPET, Cedar-Sinai software.

VII. Statistical analysis:

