Our primary endpoint will be significant stenosis for flow limiting lesions (≤ 0.8) by CT-FFR. We will derive sensitivity, specificity, NPV, PPV of CTA-cFFR compared to the reference standard of ICA with FFR for each epicardial coronary artery.

Our secondary endpoint will be the correlation of segmental PET MBF and MPR to presence or absence of a coronary artery stenosis $\geq 50\%$ diameter, and in patients with stenosis $\geq 50\%$ diameter, correlation with CT-cFFR, and ICA/ICA FFR for which we will perform a Pearson correlation coefficient. We will also compare a hybrid model of PET MPR-CTA-cFFR to ICA with FFR. Spearman's rank correlation coefficient may be used as an alternative if there are issues with the assumption of a linear model. Descriptive statistics will be used to portray demographic and clinical characteristics of study participants and clinical outcomes at 25-30-day follow-up.

CAC in each epicardial artery will be compared to regional MBF.

Sample size justification

The primary aim of this study is to estimate the sensitivity, specificity and other measures of accuracy. As such, the width of the confidence interval around these estimates are important. Based on a study by Driessens et. al, these proportions are expected to be at least 0.75. A sample size of 35 produces a two-sided 95% confidence interval with a width equal to 0.287 or (0.607, 0.893) when the proportion is 0.75. Additionally, a sample size of 35 achieves 80% power to detect a correlation of 0.45 using a two-sided Pearson correlation with a significance level of 0.05.

VIII. Time Line

Patient recruitment/Imaging exams: 4-6 months

Image and data analysis: 1 month

IX. Funding Source: Departmental**X. References**

- 1) Fihn SD et al. 2012 ACCF/AHA/ACP/AATS/PCNA/SCAI/STS guideline for the diagnosis and management of patients with stable ischemic heart disease. *Circulation*. 2012;126:e354-e471.

- 2) Kajander S et al. Cardiac positron emission tomography/computed tomography imaging accurately defects anatomically and functionally significant coronary artery disease. *Circulation.* 2010;122:603-613.
- 3) Driessen RS et al. Comparison of coronary computed tomography angiography, fractional flow reserve, and perfusion imaging for ischemia diagnosis. *J Am Coll Cardiol.* 2019;73:161-73.

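### Correlating PET flow with stenosis as present/absent at 50% discards severity; recording percent stenosis is a cheap gain, and the plan should say which correlation its r = 0.45 describes

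*Combined protocol and SAP*

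**What the plan says.** The secondary endpoint appears in the same terms in Section II (Objective) and Section VII (Statistical analysis), and it has two parts.

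- **First part:** "Our secondary endpoint will be the correlation of segmental PET MBF and MPR to presence or absence of a coronary artery stenosis" of at least 50% diameter. One variable is continuous and the other is yes/no.
- **Second part:** in patients who have such a stenosis, PET flow is correlated with CT-FFR and with invasive angiography and invasive FFR. The Pearson coefficient is named directly after this part. Spearman is offered if linearity is doubtful.

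Section VI (Image Analysis) has a cardiac CT radiologist read the cCTA "using a Vital Images workstation for epicardial coronary artery stenoses" at or above the 50% cut. It does not say that a percentage is recorded. PET flow is computed by segment.

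The sample size justification in Section VII says that "a sample size of 35 achieves 80% power to detect a correlation of 0.45 using a two-sided Pearson correlation", at a significance level of 0.05. It gives no variable pair, no expected stenosis prevalence and no unit of analysis for that statement.

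**The concern.** Percent diameter stenosis is a graded quantity. Under the cut, a 50% and a 95% lesion count as equal, and so do a normal artery and a 45% lesion. Section VI gives the cut a purpose in choosing lesions for CT-FFR, but no reason is given for using it in this correlation.

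Two things are at stake. First, a cut variable usually correlates less strongly with flow than the graded one, so a real relation is easier to miss. Section II already expects that MBF/MPR will sometimes disagree with anatomy, especially in small vessel disease. A weak correlation produced by the cut could be mistaken for that disagreement. Second, the first part cannot show whether flow falls as anatomic narrowing increases.

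**Working it through.** **Inputs from Section VII:** n = 35, r = 0.45, two-sided alpha 0.05, stated power 80%. **Assumed, because the documents do not give them:** 35 independent pairs, a bivariate-normal model, and prevalence p of stenosis of at least 50%.

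**1. The plan's own figure.** Fisher z: power = Φ(atanh(r)·√(n−3) − 1.96).
atanh(0.45) = 0.4847; 0.4847 × √32 = 2.742; 2.742 − 1.960 = 0.782; Φ(0.782) = 78.3%.
Adding the bias term r/(2(n−1)) gives 79.4%. Simulating the t-test of r (200,000 runs) also gives 79.4%. The stated 80% is reproduced for two continuous variables.

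**2. If 0.45 is the correlation before the cut.** Cutting a normal variable at prevalence p multiplies the correlation by φ(z_p)/√(p(1−p)). Example at p = 50%: 0.399/0.5 = 0.798; 0.45 × 0.798 = 0.359; atanh(0.359) × √32 − 1.96 = 0.166; Φ = 56.6%.

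| Assumed prevalence | Factor | r after cut | Power, Fisher z | Power, simulated | Before-cut r that gives 0.45 after the cut |
|---|---|---|---|---|---|
| 10% | 0.585 | 0.263 | 33.2% | 32.6% | 0.769 |
| 20% or 80% | 0.700 | 0.315 | 45.4% | 46% | 0.643 |
| 30% or 70% | 0.759 | 0.341 | 52.1% | 54% | 0.593 |
| 40% or 60% | 0.789 | 0.355 | 55.5% | 57% | 0.571 |
| 50% | 0.798 | 0.359 | 56.6% | 59% | 0.564 |

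Against 79% on the full scale, the loss is 79 − 59 = 20 to 79 − 46 = 33 points for prevalence of 20-80%. Reaching 80% power after the cut would take about 59 pairs at 50% prevalence and 66 at 30%.

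**3. If 0.45 is the correlation with the yes/no variable.** This is a point-biserial correlation, equivalent to a standardized mean difference of 0.45/√(1−0.45²)/√(p(1−p)). That is 1.01 at p = 50% and 1.26 at p = 20%. Simulated power is 81% and 79% respectively, so the 80% stands. The before-cut correlation would then be 0.564-0.643 (last column, p = 20-80%). Fisher z with the bias term gives full-scale power of Φ(1.70) = 96% to Φ(2.41) = 99%. The graded analysis gains about 96 − 81 = 15 to 99 − 79 = 20 points.

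**4. Departures from the normal model.** In 16 scenarios, stenosis was evenly spread or beta-shaped over 0-100% and flow fell linearly or only above 30-50% stenosis, with the full-scale Pearson r held at 0.45. Full-scale Pearson power was 78.5-81.7%, against 59.2-76.2% for the cut. The gain was about 8-22 points in 15 scenarios and 3.5 in one. Spearman on percent stenosis had 64.5-81.9% power and fell up to about 6 points below the yes/no analysis in right-skewed samples. In further zero-inflated, non-normal checks the Pearson gain was mostly about 3-18 points and nil in one case. It reversed only when flow dropped as a step at 50%.

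**The case against.** A reader might infer that the stated 80% is wrong and that the true power is 46-59%. The documents do not support this. The power sentence names no variable pair. A Pearson coefficient with a 0/1 variable is legitimate, and if 0.45 is that coefficient the power is about 80%. The Pearson clause also follows the second, continuous part of the endpoint, so the 80% may never have been meant for the yes/no part. The 46-59% range further needs a prevalence and a normal model that the plan does not state. This part of the objection stands in full.

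The unit is open as well. The calculations use 35 independent pairs, while flow is segmental and stenosis is read by artery. As an illustration, three arteries per patient with an intraclass correlation of 0.3 would leave about 105/1.6 ≈ 66 effective units. The attenuated r of 0.315-0.359 would then have roughly 74-85% power. Other clustering assumptions would move this either way. This too stands, and it is why the unit needs stating.

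A reader might also infer that the trial could not show whether flow falls with disease severity. That goes too far. CT-FFR and invasive FFR are graded measures already correlated with flow in patients with stenosis of at least 50%, and calcium score is compared with regional MBF. What goes unexamined is the gradient with anatomic severity.

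Finally, the graded analysis is not better in every case: Spearman can lose its advantage, and visual percentages carry reading error. This stands as a reason to keep the 50% contrast, but not as a reason to leave severity unrecorded.

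**Conclusion.** This is a cheap improvement to one part of a secondary endpoint in a pilot. It does not show that the power statement is wrong. The first part pairs a continuous PET measure with a yes/no stenosis variable and so discards anatomic severity. With 35 independent pairs, a bivariate-normal model and prevalence of 20-80%, the graded analysis has more power under either reading of 0.45: 79% against about 46-59% if 0.45 precedes the cut, or about 96-99% against about 80% if it follows the cut. With skewed or zero-heavy stenosis, or flow that falls only above a threshold, the Pearson gain is roughly 0-22 points. It becomes a loss if the true relation is a step at 50%.

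Separately, the plan should say what 0.45 refers to. If it refers to the second part analysed per patient, n = 35 holds only if every patient has a stenosis of at least 50%. At assumed subset sizes of 15, 20 and 25, power for r = 0.45 is about 41%, 53% and 64%.

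**What to change.** - **Section VI:** have the same reader record the maximal percent diameter stenosis for every epicardial artery, including those below 50%.
- **Sections II and VII:** make the Pearson correlation of MBF/MPR with percent stenosis the main analysis for the first part of the endpoint. Keep the 50% contrast as supportive, reported as a difference in mean MBF/MPR with a 95% CI.
- **Sample size justification:** state which variable pair the 80% at r = 0.45 refers to, and whether the unit is the patient or the artery. If it is the artery, say how within-patient clustering is handled.

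The cost is one number per artery on scans that are already being read, plus wording changes in three sections. The downsides are reading error in percent stenosis, a Spearman alternative that can fall below the yes/no analysis in skewed or zero-heavy samples, and lost power if flow really drops as a step at 50%. Retaining the 50% contrast limits all three.

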Subjects and Recruitment: This is a single cohort, technology assessment study. Thirty-five patients presenting with stable angina and a moderate pretest likelihood for CAD who are already scheduled to undergo ICA for the clinical indication of angina will be recruited to undergo PET-CTA-cFFR. Exclusion criteria include: Prior history of stenting, coronary artery bypass graft surgery, or myocardial infarction, unstable angina, atrial fibrillation, second or third degree atrioventricular block, class IV heart failure, iodine allergy, renal dysfunction, symptomatic asthma, and pregnancy.

Patient history will be gathered on the following: gender, age, weight, BMI, risk factors (HTN, DM, DLD, smoking), family history, and medications (statins, Beta blockers, Nitrates, ASA).

Recruited patients will undergo cCTA and concurrent N-13 ammonia stress and rest PET evaluation. Patients will undergo their clinically scheduled ICA with FFR within 2 weeks. ICA with FFR will be compared to each of these modalities alone (cCTA, CTA-cFFR, PET MBF/MPR) as well as a hybrid model of these modalities together (PET-cCTA-cFFR). Patients will be contacted by phone 24-72 hours after scanning to ask about any interval changes in health. The coordinator will also call the patient between 25-30 days following their ICA to assess for major adverse cardiovascular event (MACE) defined as hospital readmission for myocardial infarction, angina, or ventricular arrhythmia, or cardiovascular death. The protocol will be reviewed and approved by the Washington University Human Studies Committee and all patients will receive informed consent.

Patients who have already undergone a cCTA within 45 days of their planned PET/CT will not undergo the cCTA component of the research examination. Rather, their cCTA will be collected retrospectively for research evaluation.

V. Imaging Protocol:

Recruited patients will be evaluated on a Siemens Vision PET/CT scanner (128-slice Siemens Edge).

PET-CTA Examination:

If the subject has not had prior cCTA imaging, a comprehensive cardiac PET-cCTA will be performed with acquisition of PET and cCTA imaging in the same setting.

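### The stated interval width of 0.287 uses all 35 patients as denominator, but each accuracy measure is per artery and uses only a subset of arteries

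*Combined protocol and SAP*

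**What the plan says.** Section VII, under the sample size justification, sets the aim: "The primary aim of this study is to estimate the sensitivity, specificity and other measures of accuracy". It adds that for this reason "the width of the confidence interval around these estimates are important". Citing a published imaging comparison, it says "these proportions are expected to be at least 0.75", and then gives one precision figure: "A sample size of 35 produces a two-sided 95% confidence interval with a width equal to 0.287 or (0.607, 0.893").

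The number 35 comes from section IV, which plans to recruit "Thirty-five patients presenting with stable angina and a moderate pretest likelihood for CAD".

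The primary analysis, in sections II and VII, is at a different level: "We will derive sensitivity, specificity, NPV, PPV of CTA-cFFR compared to the reference standard of ICA with FFR for each epicardial coronary artery".

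Section VI limits which arteries get a CT-FFR value. For lesions of at least 50% "diameter, CT-FFR will be calculated using a computational flow/AI FFR program (Siemens") is the planned step; no CT-FFR value is planned below that threshold.

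The plan gives no expected number of evaluable arteries, no expected share of FFR-positive arteries, no denominator for any of the four measures, no interval method for the analysis and no allowance for several arteries in one patient.

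**The concern.** An interval of 0.287 at 0.75 needs about 35 units in the denominator of that one proportion. None of the four measures is planned that way. Sensitivity is a proportion of FFR-positive arteries, specificity of FFR-negative arteries, PPV of test-positive arteries and NPV of test-negative arteries. The count of patients is none of these.

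The per-artery wording can mean two things: a separate accuracy table for each artery (at most one unit per patient, so at most 35), or one table that pools arteries over patients (for example 105, if three per patient are all evaluable). Neither makes 35 the common denominator.

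Interval width is the plan's only justification of the sample size for its primary aim, so a reader will take 0.287 as the expected precision of each measure. If arteries are pooled, an interval that treats one patient's arteries as independent would also be too narrow when results within a patient are positively correlated.

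**Working it through.** **Inputs from the plan:** 35 patients (section IV); proportion 0.75 and "two-sided 95% confidence interval" (section VII); per-artery analysis (sections II and VII). **Assumptions, not in the plan:** share of arteries that are FFR-positive, number of evaluable arteries, within-patient correlations (ICC).

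**1. The plan's figure.** Wald width = 2 × 1.96 × √(p(1−p)/n). With p = 0.75 and n = 35: 3.92 × √(0.1875/35) = 0.287, interval 0.607 to 0.893. This reproduces the plan, with all 35 patients as one denominator.

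**2. Arteries analysed separately (at most 35 units).** FFR-positive and FFR-negative units sum to at most 35, so the smaller group is at most 17. At p = 0.75 and n = 17: 3.92 × √(0.1875/17) = 0.412 (Wilson 0.383). This bound needs no assumed prevalence. A width of 0.287 for both sensitivity and specificity would need 35 + 35 = 70 units, evenly split.

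Wald widths at 0.75 by assumed prevalence:

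| FFR-positive | Positive / negative units | Sensitivity | Specificity |
|---|---|---|---|
| 20% | 7 / 28 | 0.64 | 0.32 |
| 30% | 10.5 / 24.5 | 0.52 | 0.34 |
| 40% | 14 / 21 | 0.45 | 0.37 |
| 50% | 17.5 / 17.5 | 0.41 | 0.41 |

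Non-integer counts are approximations. For whole counts near 30%, a 10/25 split gives 0.54/0.34 and 11/24 gives 0.51/0.35.

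**3. PPV and NPV.** With sensitivity and specificity 0.75 and 40% FFR-positive, the test-positive share is 0.4 × 0.75 + 0.6 × 0.25 = 0.45. PPV = 0.30/0.45 = 0.667 and NPV = 0.45/0.55 = 0.818. Of 35 units, 15.75 are test-positive and 19.25 test-negative, giving Wald widths of 0.47 and 0.35.

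**4. Arteries pooled, treated as independent.** Wald widths at 0.75:

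| Evaluable arteries | FFR-positive | Sensitivity | Specificity |
|---|---|---|---|
| 105 | 20% | 0.37 | 0.19 |
| 105 | 30% | 0.30 | 0.20 |
| 105 | 40% | 0.26 | 0.21 |
| 70 | 40% | 0.32 | 0.26 |
| 35 | 40% | 0.45 | 0.37 |

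With 105 arteries, sensitivity is wider than 0.287 when fewer than 35 of 105 (one third) are FFR-positive, and narrower when more are. PPV/NPV with 105 arteries at 40% are 0.27/0.20.

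**5. Arteries pooled, clustered by patient.** Simulation: 35 patients, beta-binomial FFR status and beta-binomial correctness of the test, one correctness effect per patient, 20,000 replicates, width = 2 × 1.96 × SD. At 40% FFR-positive:

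| Arteries per patient | Correctness ICC | FFR-status ICC | Sens | Spec | PPV | NPV |
|---|---|---|---|---|---|---|
| 3 | 0.2 | 0 | 0.28 | 0.24 | 0.30 | 0.22 |
| 3 | 0.2 | 0.3 | 0.29 | 0.24 | 0.33 | 0.24 |
| 3 | 0.5 | 0.3 | 0.33 | 0.28 | 0.36 | 0.26 |
| 2 | 0.2 | 0 | 0.34 | 0.28 | 0.35 | 0.26 |
| 2 | 0.2 | 0.3 | 0.34 | 0.28 | 0.37 | 0.27 |

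With three arteries per patient, correctness ICC 0.2 and status ICC 0.3, the sensitivity width is about 0.34 at 30% FFR-positive and about 0.41 at 20%.

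At 40% and status ICC 0.3, an unclustered 95% Wilson interval for sensitivity covers about 93% at correctness ICC 0.2 and about 89% at 0.5, against 95.5% at correctness ICC 0.

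**The case against.** The strongest reply is that the clearly unfavourable result belongs to one reading only. If arteries are pooled, 105 are evaluable and 40% are FFR-positive, then even with modest clustering (correctness ICC 0.2) 0.287 is about right for sensitivity and conservative for specificity. This stands: the point is not that precision is generally worse than stated, and under pooling the direction is unknown.

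Second, the plan treats 0.75 as a floor. At 0.90, 17 units give a Wald width of 0.285. That is true, but 35 units at 0.90 would give 0.199, so the ratio of √(35/17) = 1.43 remains.

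Third, the PPV of 0.67 used above lies below the plan's floor. If PPV is set to 0.75 on the same 15.75 units, the width is 0.43 instead of 0.47. But sensitivity and specificity at 0.75 with 40% FFR-positive imply 0.67, so those inputs and the floor cannot both hold for PPV.

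Fourth, this is a single-cohort pilot with no precision target and no hypothesis test on accuracy, and the plan does not commit to treating arteries as independent. This limits the consequence, but it does not make 35 the denominator of any of the four measures.

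**Conclusion.** The concern holds. The arithmetic behind 0.287 is right, but the denominator does not match the planned analysis under either reading of the per-artery wording.

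- **Separate arteries:** for at least one of sensitivity and specificity, the width at 0.75 is at least 0.41 (Wilson about 0.38). This rests only on the plan's 35 patients and its 0.75.
- **Pooled arteries:** over the assumptions examined, with 20% to 40% FFR-positive and 35 to 105 evaluable arteries, the sensitivity width runs from about 0.26 to 0.45. These values are illustrations, because the plan supplies no prevalence, artery count or correlation.

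Confidence is high on the denominator and lower on the assumption-driven widths. This is a misstated expectation of precision in a pilot, not a failed criterion. It should be fixed because it concerns the primary aim and leaves the unit of analysis and interval method open until the data are seen.

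**What to change.** Keep 35 patients and amend section VII as follows.

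1. **State the unit:** whether arteries are analysed separately or pooled over patients, and how arteries below the 50% threshold, which get no CT-FFR value, enter the accuracy tables.
2. **Replace the single 0.287** with a width for each of the four measures, over a stated range of FFR-positive prevalence and evaluable arteries, all labelled as assumptions. As an example at 40% FFR-positive with sensitivity and specificity 0.75, in the order sensitivity/specificity/PPV/NPV:
   - separate, 35 units, Wilson: 0.42/0.35/0.42/0.33;
   - pooled, 105 arteries, correctness ICC 0.2, status ICC 0 to 0.3: 0.28–0.29/0.24/0.30–0.33/0.22–0.24;
   - pooled, 70 arteries, same ICCs: 0.34/0.28/0.35–0.37/0.26–0.27.

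   The range should also cover prevalence of 20% to 30% and fewer evaluable arteries, where sensitivity is wider. The separate and pooled lines use different width formulas and are not strictly like for like; the final table should use one method within each reading.
3. **Name the interval method:** Wilson or exact if separate; if pooled, a patient-level method such as a cluster bootstrap, or GEE with a small-sample correction because there are only 35 clusters.

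The cost is a few sentences and a routine method, with no extra patients. The stated precision may look less favourable, mainly under the separate-artery reading; under pooling some widths would be narrower than 0.287.
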